# **Statistical Analyses**

Analyses will be completed with IBM SPSS v. 23. Means, medians, standard deviations (SD) will be compared between subgroups on the measures using conventional cut-off points for each of the symptoms will be compared.

Specific Aim 1 will be tested by comparing the number of participants in each condition meeting the study definition of compliance (having completed 80% sessions). We will also determine the effectiveness of our sham procedures to ensure blinding, as tested by comparing those who accurately identified the sham condition. We will assess whether the frequency or type of side effects differ between the three conditions and whether they occur at the same rate as reported from studies of inclinic administration.

Specific Aim 2 will be to determine preliminary signals for efficacy, and to have pilot findings to determine necessary sample sizes for an adequately-powered clinical trial. For each participant, change scores will be calculated between baseline and study end scores on measures of fatigue and cognitive functioning. These difference scores will then be described and compared between groups (t-tests and ANOVA related analyses) to determine signals of efficacy.

Cognitive performance will be evaluated for those who completed at least 18 sessions. We conservatively plan for comparison of 15 participants in each group, allowing for up to 33% dropout. While both cognitive remediation groups are expected to improve with cognitive training, we hypothesize that the active tDCS condition will gain one standard deviation (of the published normative mean) or more in score than the sham condition and that the group with active tDCS paired with non-adaptive puzzle and board games will neither improve nor decline.

Secondary outcomes will be used to compare the groups in change in performance on the additional measures listed in Table 2. These are the most commonly-used outcome measures in MS trials

. While important to include, they will not be the primary outcome due to strong susceptibility of improvement with practice effects over repeated administrations in MS samples. In addition, performance on the WM CT will be analyzed across training sessions, including time to advance to a new level and overall levels achieved, parameters shown to improve with tDCS. Similar analysis as what have been planned for the primary outcome will be performed for comparing the change in these secondary outcomes between two groups.

MS clinical features (age, gender, MS subtype, treatment type, disease duration) will be compared by correlational analysis.

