# IV. SPECIFIC AIMS

Specific Aim 1: To test the feasibility of a randomized, controlled remotely-supervised tDCS clinical trial protocol developed specifically for use in MS. Participants (n=85) will be randomly assigned to receive 40 x 20-minute sessions of either active (up to 2.5 mA) paired with cognitive remediation, to two separate control conditions. The first is an active tDCS condition paired with non-adaptive, traditional puzzle and board games and will act as this study's negative control. The second control will act as the study's positive control and will be sham tDCS paired with cognitive remediation. Each study session, regardless of study arm, will be followed by an additional 10 minute computerized training sessions post-stimulation. Each study arm will complete 40 sessions over eight weeks.

The *primary outcome* for feasibility will be the number of participants completing at least 80% or n=32of the targeted 40 sessions. Secondary outcomes will be comparison of tolerability and participant- reported side effects between the two treatment arms.

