#### A pilot study of remotely-delivered (tDCS) combined with cognitive training in adults with multiple sclerosis (MS) (S15-01189)

fatigue (pre- and post-								
Visual analog scale for pain (pre-, early-, mid- and post-session)		Х	X	X	X	X		
Tolerability questionnaire - administered by study staff (pre- and post-session)			X		X			
Safety and tolerability questionnaire –self-report (pre- and post-session)			X		X			
Score for Computerized cognitive games (daily)*			Х		Х			
Daily assessment of sleep			Х		X			
Patient and Caregiver Questionnaires*						Х		
Participant Evaluation of Study Procedures*			Х	Х	X	Х		
Count of successful tDCS sessions (confirmation code by session days)			X	X	X	X		
Optional measures that may b	e exclude	d based on s	tudy persor	nel judgem	ent are indicat	ed by an aster	risk.	

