# e)Analytic Plan:

Specific Aim 1 is to determine feasibility; to be measured by the number of participants successfully completed using the proposed protocol for training and monitored administration. As would be expected, there is a high rate of compliance for in-clinic tDCS administration and therefore remotely-supervised administration should be designed to be similarly compliant. Study success will be defined by 80% participants having completed 80% sessions, shown to be the target compliance for previous tDCS studies. We will also determine the effectiveness of our sham procedures to ensure blinding, as tested by comparing those who accurately identified the sham condition. We will assess whether the frequency or type of side effects differ between the active and control conditions and whether they occur at the same rate as reported from studies of in-clinic administration. Secondary outcomes will be tolerability, participant-reported adverse events, and comparisons of active and control conditions on these measures.

Specific Aim 2 will be to determine preliminary signals for efficacy, and to have pilot findings to determine necessary sample sizes for an adequately-powered clinical trial. For each participant, change scores will be calculated between baseline and study end scores on measures of fatigue and cognitive functioning. These difference scores will then be described and compared between groups (t-tests and ANOVA related analyses) to determine signals of efficacy for active tDCS paired with cognitive remediation vs. active tDCS paired with non-adaptive puzzle and board games vs. sham tDCS paired with cognitive remediation.

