#### Monitoring

We will utilize operating procedures for reviewing patient safety data and source data generated from this study. This will include weekly meetings between the PI. Co-investigators, and study coordinator. At these meetings, the entire research team will review the clinical ratings, assessments, clinical course, and medical records for each subject. Consideration of dropping any patient from the study for any reason will be discussed. If after the completion of the first 10 subjects the compliance is significantly less in one or more arm of the study relative to our previously observed compliance rates, the study will be put on hold and reviewed. Based on the extensive body of literature using tDCS across a range of conditions, and our initial participants studied to date (completed at Stony Brook Medicine, we have had >94% compliance in the active condition. Therefore, this discrepancy in compliance is not expected. We would define discrepancy in compliance as >50% difference in mean number of visits completed and/or 50% difference in number of "completers" in each condition (defined by completing at least 50% of n=5/10 sessions). If there is significantly poor compliance in the active session, we will be able to identify reasons including tolerability as well as symptom experiences. Tolerability is measured before, during and after each session and all participants will be monitored for all sessions. Safety is carefully addressed in our protocol with a series of stop criteria and clearly defined action items.

Specific attention will be given to data quality and timeliness, HIPAA-complaint, safe storage of data, and data backup of electronic source data. Attention will also be given to participant recruitment, accrual and retention, participant risk versus benefit, adverse events, and other factors that can affect study outcome, including scientific or therapeutic developments that may have an impact on the safety of the participants or the ethics of the study.

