# **Exploratory Aim**

**Exploratory Aim**: We will test the feasibility of remotely-supervised in-home self-administered tDCS combined with computerized cognitive activities in **Parkinson's Disease (PD).** Participants (n=30) will be trained to administer active tDCS and complete a cognitive training activity in their home under remote supervision by study staff.

Hypothesis 1: Remotely-supervised in-home delivery of the tDCS combined with computerized cognitive activity is a safe and feasible treatment for impairment in Parkinson's disease.

Primary outcome will be number of days of successful tDCS delivery. Secondary outcomes will be tolerability and participant-reported adverse events, fatigue and mood.

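### Aim 1 compares arms only on reaching 32 of 40 sessions; adding a comparison of the recorded session count would pick up modest attendance gaps that this cut usually misses

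*Combined protocol and SAP*

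**What the plan says.** Section IV (Specific Aim 1) makes the primary feasibility outcome the number of participants "completing at least 80% or n=32of the targeted 40 sessions". Section V(e), Analytic Plan, sets the benchmark for the trial as a whole: "Study success will be defined by 80% participants having completed 80% sessions". It justifies the threshold as "shown to be the target compliance for previous tDCS studies".

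Section IX, Statistical Analyses, then uses the same threshold to compare arms: Aim 1 "will be tested by comparing the number of participants in each condition meeting the study definition of compliance (having completed 80% sessions"). No test, significance level or power is given.

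The uncut data exist. Table 2 lists "Count of successful tDCS sessions (confirmation code by session days") as a recorded measure. The count is used directly in two other places. The hold rule under Monitoring (section IX) looks at the "difference in mean number of visits completed" after the first 10 subjects. In the Parkinson's cohort (section XI), "Primary outcome will be number of days of successful tDCS delivery".

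For the MS cohort, the nearest text to a between-arm analysis of the count is generic. One line in section IX compares means, medians and SDs on the measures. Another compares change in performance on the additional Table 2 measures, which does not fit a session count because a count has no baseline value.

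**The concern.** The 80% threshold is chosen and defended as an overall success criterion. Carried over to the comparison of arms, it reduces a 0-40 count to yes or no at a point that most participants are expected to exceed. In the team's feasibility study (section II), 95% completed at least 8 of 10 sessions. An arm could lose two or three sessions per person while most of its members stay at or above 32, and the planned comparison would then usually show no difference.

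The trial is meant to establish a protocol for later controlled trials. A consistent difference between arms in sessions received is a difference in exposure that the planners of the next trial would want estimated, and the data for it are already collected.

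**Working it through.** **Inputs from the documents**
- Cut-off: 0.80 × 40 = 32, which reproduces the protocol's figure.
- Arm size: 85 participants, 1:1:1, so 85/3 = 28.3, or about 28 per arm.
- Pilot attendance: 192 sessions in 20 people planned for 10 each, so 192/(20 × 10) = 96%.
- Pilot compliance at the 80% level: 95% (19 of 20).

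**Assumptions, because the documents are silent**
- Two-sided 5% for each pair of arms.
- Attendance follows a beta-binomial distribution over 40 sessions, with within-person correlation 0.1 (varied from 0.03 to 0.2).
- A fraction of participants stop early, at a uniformly distributed time.

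**Step 1. What the complier comparison can detect**

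For two proportions, power = Φ{(|p1 − p2| − 1.96·√[2p̄(1 − p̄)/n]) / √[(p1(1 − p1) + p2(1 − p2))/n]}. For 95% versus 80% with n = 28, p̄ = 0.875 and this is Φ{(0.15 − 1.96 × 0.0884)/0.0861} = Φ(−0.27) = 39%. Exact Fisher power is 21%.

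| Compliers | Normal approximation | Fisher |
|---|---|---|
| 95% v 85% | 24% | 8% |
| 95% v 80% | 39% | 21% |
| 95% v 75% | 56% | 39% |
| 95% v 65% | 82% | 74% |

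For 80% power at 95% versus 80%, 76 per arm would be needed. Sample size therefore explains part of the weakness. Step 2 isolates the part due to the cut, because n is the same for every test.

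**Step 2. Cut versus count, 28 per arm**

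Mean sessions = 40 × attendance × (1 − s/2), where s is the fraction stopping early (on average halfway). The reference arm has 96% attendance and s = 5%: 40 × 0.96 × 0.975 = 37.4. At 92% attendance the mean is 40 × 0.92 × 0.975 = 35.9, and at 88% it is 40 × 0.88 × 0.975 = 34.3. With 96% attendance and s = 30% it is 40 × 0.96 × 0.85 = 32.6.

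| Pattern in the other arm | Mean sessions | Fisher, cut | Chi-square, cut | Welch, count | Wilcoxon, count |
|---|---|---|---|---|---|
| No difference | 37.4 v 37.4 | 0.4% | 4.2% | 3.3% | 4.8% |
| Scattered misses, 92% | 37.4 v 35.9 | 3% | 12% | 21% | 48% |
| Scattered misses, 88% | 37.4 v 34.3 | 18% | 36% | 56% | 92% |
| Early stopping only, 5% v 30% | 37.4 v 32.6 | 35% | 52% | 55% | 36% |

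In the 88% row, about 78% of the worse arm still reaches 32 sessions. With correlation 0.03 and 0.2, that row gives chi-square 28% and 31%, and Wilcoxon 99% and 77%.

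**Step 3. A second set of assumptions**

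Here scattered misses have correlation 0.05 to 0.3 and no stoppers. Early stoppers, where modelled, leave somewhere between 1 and 31 sessions.
- Scattered, 38 v 35 sessions: Fisher 16-20%, Pearson chi-square 30-46%, t-test 43-96%, Mann-Whitney 64-97%.
- Scattered, 38 v 32 sessions: Fisher 61-96%. The cut usually finds this gap.
- Mixed (stopping 5% v 15%, attendance of the rest 97% v 92%): Fisher 15%, Pearson 36%, t-test 59%, Mann-Whitney 96%.
- Stopping only, 5% v 25% (37.7 v 33.1 sessions): Fisher 39%, Pearson 59%, t-test 50%, Mann-Whitney 26%.

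Both sets agree in direction. The count gains for scattered or mixed patterns. Under pure stopping, means and the cut are about level, and ranks are the weakest or equal to Fisher.

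**The case against.** The strongest reply is that the cut is the declared primary outcome and has a stated rationale. Aim 1 asks whether people receive an adequate course, and an arm averaging 34 sessions is still mostly compliant on that definition. Nothing in the documents treats three sessions as important, and the only stated discrepancy threshold is above 50%, in the hold rule. This stands, and it is why the complier comparison should remain primary.

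The size of the loss also depends on an assumed pattern. What the documents describe is mostly stopping: the one pilot participant below 8 of 10 discontinued, stop criteria lead to discontinuation, and section IX allows up to 33% dropout for the cognitive analysis. Under pure stopping the cut holds its own. This stands too.

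The inputs can also be questioned. The 96% already includes the pilot participant who stopped, so adding 5% stoppers counts that person twice. Removing the duplication does not remove the Wilcoxon gain for scattered misses. The pilot ran 10 sessions over two weeks, not 40 over eight, so expecting most participants above the cut is an extrapolation. Fisher is conservative here (0.4% rejection under no difference) and the plan does not name it, so the chi-square column is the fairer benchmark.

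A reader might infer that an attendance problem would pass unnoticed. The documents do not support that: sessions are supervised by video, tolerability is recorded at each one, side effects are compared between arms, and retention is reviewed at weekly meetings. What is missing is a planned estimate of the between-arm difference in sessions.

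**Conclusion.** The point holds for modest gaps. With about 28 per arm, a difference of about 1.5 to 3 sessions per person from scattered misses would usually be missed by the complier comparison. At 37.4 versus 34.3 sessions, power is about 18% (Fisher) or 36% (chi-square), against 56% for a comparison of means and 92% for a rank test. These figures assume a beta-binomial spread, correlation 0.1, 5% early stoppers and a two-sided 5% level. The direction was the same in every scattered or mixed pattern tried, but the size is not fixed by anything in the documents.

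Two stronger readings are tempting and do not hold. A reader might infer that clear attendance differences in general would be missed. Gaps of about 6 or more sessions from scattered misses, or about 30 points or more in compliers, are usually found. A reader might also infer that a rank test should replace the complier comparison. If arms differ only by early stopping, that would lose power (36% against 52% by chi-square). The case is for adding an analysis of the count beside the declared one.

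**What to change.** Keep the 80%/80% rule as the success criterion and the between-arm complier comparison as the primary Aim 1 analysis. In section IX, Statistical Analyses, under Specific Aim 1, add a between-arm comparison of sessions completed (0-40) per randomised participant. Report it as the mean difference for each pair of arms with its confidence interval, with a rank test as a supporting analysis (Kruskal-Wallis, then Wilcoxon for pairs). Give the number stopping early in each arm alongside. The mean difference is the better lead because it beats the cut for scattered and mixed patterns and is about level with it under pure stopping.

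The cost is a sentence or two in the analysis section and no new data. The downside is one more secondary comparison to report and interpret, which should be labelled as secondary.

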**c)** Randomization: Participants will be assigned to each condition in a 1:1:1 Stratified randomization procedure. Participants will be matched according to the degree of cognitive impairment (Symbol Digit Modalities test or SDMT score) and neurologic (motor) impairment (Expanded Disability Status Scale or EDSS score). Participants will be randomized to either the active tDCS condition paired with cognitive remediation or one of the two control conditions. The positive control condition will consist of cognitive remediation paired with sham tDCS and the negative control condition will consist of active tDCS with non-adaptive puzzle and board games using block randomization of permuted block sizes 3 and 6, based on our experience in cognitive remediation trials. SDMT performance will be categorized compared to published age-normative means (>0.99 SD, 1 to 2 SD and 2 to 3 SD below mean) and EDSS score will be categorized as mildly or moderately impaired (0 to 3.0 vs. 3.5 to 8.0).

d)*Outcome Measures:* Before and after each session, participants will complete brief measures to monitor for any stimulation-related events as well as mood and fatigue. In addition a pain scale will be administered during the session. Participants will also complete baseline and study-end inventories of mood and fatigue and complete a brief battery of cognitive tests including the Brief International Assessment of Cognition in MS or BICAMS, to help guide power estimates for the future trials. A summary of outcome measures can be found in Table 2.

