# VI. METHODS AND PROCEDURES

All remotely-supervised sessions will be completed while connected to a video session with the study technician. The protocol is designed to have a decision-tree series of checkpoints that must be met in order to proceed at each step (Figure 2). These checkpoints address compliance (attendance, ability to complete the procedures as instructed, following the study guidelines) and tolerability (at any time, if any predefined events are reported). Following state of the art in tDCS research, devices will be programmed in advance by the PI to provide either active or sham sessions following current standards for blinding. During a sham session, the device is programmed to ramp up to the desired intensity (target 2.5 mA) and ramp down for the initial 60 seconds, with no current delivery during the following 18 minutes of the session, and then current is ramped up and down for 60 seconds at the end of the session. These brief periods of stimulation serve to mimic the effects of a true stimulation session. Both participants and study coordinator (who administers study outcome measures) will be blinded, and will be asked to guess the assigned condition at study end.

The PI will not be blinded to study condition. The PI or an un-blinded study technician will preprogram devices according to randomization and then provide to the study coordinator for each participant. That is, the study coordinator and participant will be blinded to which condition programmed to the assigned device. All procedures will be the same for all three conditions. Adverse events will be addressed in either condition, and the study PI will always know the assigned condition for each participant.

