#### VII. SUBJECT SELECTION

#### **Characteristics of the Research Population**

We will enroll a total of n=85 adults (ages 18 and over) with confirmed MS. Participation will be open to those with all subtypes and levels of disability who meet the eligibility criteria as below.

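### The blinding check is defined only by correct identification of sham, with no comparator; each natural reading can give the wrong verdict, and no analysis of active-arm guesses is named

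*Combined protocol and SAP*

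**What the plan says.** The blinding analysis is one clause, given twice. Section V(e), Analytic Plan, reads "We will also determine the effectiveness of our sham procedures to ensure blinding, as tested by comparing those who accurately identified the sham condition". Section IX, Statistical Analyses, repeats it under Specific Aim 1: "as tested by comparing those who accurately identified the sham condition". Neither place says what is compared with what, which guess rate counts as chance, which test is used, or what result would count as adequate blinding.

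Section VI, Methods and Procedures, covers data collection. Participants and the study coordinator "will be blinded, and will be asked to guess the assigned condition at study end". Guesses from the active arms will therefore exist, but neither analysis section says how they are used.

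Section V(c), Randomization, sets the structure: "Participants will be assigned to each condition in a 1:1:1 Stratified randomization procedure". It adds: "The positive control condition will consist of cognitive remediation paired with sham tDCS and the negative control condition will consist of active tDCS", the latter with puzzle and board games. Two arms receive active current and one receives sham, which is 2:1 overall but 1:1 within the two cognitive-remediation arms. Section VII gives the MS sample: "We will enroll a total of n=85 adults (ages 18 and over) with confirmed MS".

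**The concern.** Accuracy of guessing mixes two things: how much participants know, and which answer they favour when they know nothing. If blinded participants favour 'active', active participants are right more often than sham participants without any unblinding. If participants in every arm know their assignment equally well, their accuracies match and comparing them shows nothing. If only the sham arm is examined, what active participants know never enters.

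The effectiveness of the sham is a stated Aim 1 result, and the study exists to establish a protocol for later double-blind trials. Aim 2 compares arms on fatigue, using participant-rated scales such as the Fatigue Severity Scale (Table 2), for which knowledge of assignment matters most. A wrong blinding verdict would affect how those comparisons are read and how the next trial is designed. Because the comparison is undefined, its form could also be settled after the guesses have been seen.

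**Working it through.** The plan gives no figure for this check, so there is nothing to reproduce. The question is how each reading of the clause behaves when the truth is known.

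**Inputs**
- From Section VII and Section V(c): 85 MS participants at 1:1:1. 85/3 = 28.3, so about 28 sham and 57 active (28 per arm in a two-arm contrast).
- From Section IX: 15 per group as a lower scenario, giving 15 sham and 30 active. The plan states this figure for the cognitive comparison.
- Assumed: two-sided alpha 0.05.
- Assumed: q, the probability of saying 'sham'. Perfect blinding means that q is the same in every arm. The value q = 1/3 matches the allocation; 0.20 to 0.50 is shown as a range.

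**Method.** Exact rejection probability: sum the binomial probabilities of all pairs of counts for which the test gives p ≤ 0.05. Pearson chi-square is used unless stated.

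**Reading 1: percent correct in sham vs percent correct in active**

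Under perfect blinding, expected accuracy is q in sham and 1 − q in active. At q = 1/3 that is 33% vs 67%, although nobody knows anything.

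| q | 28 vs 57 | 15 vs 30 | 28 vs 28 |
|---|---|---|---|
| 0.20 | about 100% | 98% | about 100% |
| 1/3 | 83% | 56% | 70% |
| 0.40 | 40% | 24% | 31% |
| 0.50 | 5% | 5% | 5% |

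Hand check at q = 1/3, 28 vs 57:
- Pooled accuracy = (28 × 0.333 + 57 × 0.667)/85 = 0.557.
- Null SE = √(0.557 × 0.443 × (1/28 + 1/57)) = 0.1146.
- Alternative SE = √(0.222/28 + 0.222/57) = 0.1088.
- Power ≈ Φ((0.333 − 1.96 × 0.1146)/0.1088) = Φ(1.00) = 0.84, against the exact 0.83 (Fisher's test: 0.79).

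Opposite error: with both groups 90% correct, the rejection probability is 4% at 28 vs 57. With both 80% correct it is 5%.

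**Reading 2: sham-arm identifications only (n = 28, exact binomial)**
- Reference 50%, sham participants at 50%: rejects in 3.6%, whatever the active arms know, even if all active participants are correct.
- Reference 50%, q = 1/3: rejects in 38%, but because identification is below chance, which is not evidence of unblinding.
- Reference 1/3, q = 0.50: rejects in 43%, above chance, with perfect blinding.

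**Alternative: compare the proportion giving a particular guess between arms**
- Perfect blinding, q = 0.20 to 0.50: rejects in about 5% at 28 vs 57, 15 vs 30 and 28 vs 28.
- Both groups 90% correct: 90% vs 10% guess 'active'. The rejection probability is about 1.00, including at 28 vs 28.

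**Which arms to compare.** Games are paired only with active current. If every games participant says 'active' and the two remediation arms are truly blind, pooling the active arms makes this comparison reject in 45% (q = 1/3) to 66% (q = 0.50). Restricting it to the two remediation arms brings that back to about 5%.

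**The case against.** The strongest reply is that the clause is too thin to support a charge that a stated test is wrong. Because the comparison is undefined, the 83% belongs to one reading under one guessing assumption. That stands, and the defect is underspecification.

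A reader might make four further inferences that the documents do not support.

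- *That one and the same check fails in both directions in the obvious case.* If 95% of active participants know their assignment and sham participants identify sham 33% of the time, comparing accuracy does detect it, with probability about 1.00 at 28 vs 57. That case is missed only when the sham arm is examined alone. Comparing accuracy misses a different case, in which both groups are equally accurate.
- *That the 2:1 ratio causes the problem.* It makes a lean towards 'active' plausible, but comparing accuracy at 28 vs 28 with q = 1/3 still rejects in 70%. The failure with equal accuracy does not depend on the ratio.
- *That blinded participants will lean towards 'active'.* The documents do not show what participants are told about arms or odds. Someone told the full structure might think 50/50 in a remediation arm and near-certain 'active' in the games arm. At q = 0.50 the false alarm under reading 1 disappears.
- *That the trial's blinding is inadequate.* Nothing here bears on that; the point is only whether the check could tell.

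It is also fair that no success rule depends on this check (study success is session completion), that Aim 2 seeks preliminary signals, and that a sensible table could be produced from the data as collected. This limits the consequence but does not supply the missing analysis.

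**Conclusion.** The point holds as a gap in specification with a better method at hand. The plan bases its blinding verdict on correct identification of sham, names no comparator and names no use of active-arm guesses. Comparing accuracy rejects under perfect blinding in 83% of trials at q = 1/3 (28 vs 57), 56% at 15 vs 30, 40% at q = 0.40 (28 vs 57) and 5% at q = 0.50; it also passes gross but equal unblinding (4% rejection at 90% correct in both groups). Examining the sham arm alone cannot reveal unblinding confined to the active arms. These sizes rest on assumed guess rates and an assumed two-sided alpha of 0.05, with guesses treated as independent and all 28 and 57 participants guessing. The plan should be amended before the guesses are examined by arm, because sham effectiveness is a reported Aim 1 result.

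**What to change.** Replace the clause in Sections V(e) and IX with a defined analysis:

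1. Tabulate guesses (active, sham, don't know) for each of the three arms.
2. As the main test, compare the proportion guessing 'active' between active tDCS with cognitive remediation and sham tDCS with cognitive remediation. State the test, alpha and handling of 'don't know'.
3. Report a blinding index per arm with a 95% CI, for example Bang's: (correct − incorrect)/number in the arm. Read the arms together. At q = 1/3 with perfect blinding the expected values are +0.33 in active and −0.33 in sham, which reflects a shared lean and not knowledge.
4. Report the games arm separately, because it is always paired with active current.
5. Analyse the coordinator's guesses in the same way, separately from participants' guesses.

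The cost is a few sentences and, if not already offered, one extra response option. No visit or measure is added.

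There is one limit to state alongside the result. With about 15 to 28 per arm, the main test has modest power for partial unblinding. For 95% vs 67% guessing 'active', Fisher's test has 69% power at 28 vs 28 and about 35% at 15 vs 15. A non-significant result should therefore be reported with its interval and not as proof that blinding held.
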